To evaluate the effects of the intervention on other domains of cognition that are commonly-impaired in MS, we will apply the MACFIMS neuropsychological battery [45] as exploratory outcomes. This includes valid and reliable tests of learning and memory [46,47], executive function [42], verbal fluency [48], and spatial perception [48]; the SDMT and PASAT further are included in the MACFIMS. As has been recommended for administration of MS-specific neuropsychological batteries, we will apply a near-vision test (e.g., Rosenbaum Pocket Vision Screener) during screening to ensure that visual acuity is adequate (i.e., corrected vision better than 20/80) to perform the tests as intended [45]. This inclusion criterion is not expected to greatly affect enrollment. We further will apply a short neuropsychological test of IQ (i.e., WTAR). For all neuropsychological tests, alternate forms will be applied at each testing session to minimize the effects of practice on cognition.

Brain Function (thalamocortical resting-state functional connectivity): Participants will undergo neuroimaging, which will include structural imaging as well as a resting-state scan. The MR instrument that will be used is an FDA-approved Siemens Skyra 3T clinical imager housed in the Rocco Ortenzio Neuroimaging Center. The structural imaging scan will be performed to measure thalamic and frontal cortex volume, and the resting-state scan will be performed in order to measure functional connectivity between the thalamus and frontal cortex. These two scans will collectively last approximately 30 minutes. Importantly, all MRI processing and analyses will be performed by [name], who will be blinded to condition. To our knowledge, this is among the first exercise randomized controlled trials in any population to include this additional level of rigor to enhance the proposed trial's reproducibility.

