- Functional tests:
 - Community participation:
 - CIQ: See attached questionnaire
 - Activities of daily living:
 - Lawton-Brody IADL Scale: See attached questionnaire
 - Quality of life:
 - MSIS-29: See attached questionnaire
 - Walking Mobility:
 - LSMA: See attached questionnaire

- MRI behavioral task practice:
 - Participants will sit at a laptop outside of the scanner and complete 1 trial of the mLC (a version of the Letter Comparison Task wherein participants indicate if two strings of letters are the same or different).
- MRI protocol:
 - Participants will undergo functional, diffusion-weighted, and structural magnetic resonance images of the brain. The MR instrument that will be used is an FDA-approved Siemens Skyra 3 T clinical imager.
 - The MRI is for research purposes only, and not part of a participant's clinical care
 - The MRI will not involve any dye/contrast
 - Data are acquired using an FDA-approved head coil.
 - Data are acquired with acquisition strategies, or pulse sequences, that include both standard product sequences by Siemens and customized sequences designed by [name] at Kessler Foundation through the manufacturer-provided, and FDA approved, sequence development environment.
 - Pulse sequences are computer code and tell the MRI scanner when to emit radio frequency energy and how to sample the data space in order to form an image.
 - Examples of different data space sampling strategies include evenly-spaced checkerboard grid sampling and sampling data along a spiraling trajectory.
 - Subjects will wear disposable earplugs and full-ear headphones to reduce scanner noise during all scans.
 - A series of functional, diffusion-weighted, and structural MRI images will be acquired, which are necessary for comparing functional connectivity findings with brain structure.
 - Participants will complete the modified Letter Comparison task while in the scanner via a back-projection screen located at the head of the MRI scanner.
 - Each MRI session will take approximately 1 hour
 - The subject will be free to quit the study at any time, either by indicating their desire to do so directly to the investigator or by pressing a button while in the MRI machine that alerts the technologist who is running the scanner

Participants will be remunerated \$100 in the form of a check following the completion of Baseline Visit 2.

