5.2.4 Randomization. Following baseline testing, participants will be randomly assigned to either the exercise training or active control condition using concealment and a computerization. Participants further will be blinded to condition (i.e., unaware that the treadmill walking exercise training condition represents the experimental condition and the stretching-and-toning condition represents the active control condition).

5.2.5 Experimental Condition: Treadmill Walking Exercise Training. The experimental condition will include 3-months of supervised, progressive light, moderate, and vigorous intensity treadmill walking exercise training based on ACSM guidelines for maximizing adaptations with exercise training. This will occur at Kessler Foundation. Exercise intensities will be prescribed based on percent oxygen consumption reserve (% VO₂R) using values derived from the baseline graded exercise test. See the table below for the exact exercise prescription. The exercise progression in terms of duration and intensity will involve 3 distinct stages: (a) the initiation stage; (b) the improvement stage; and (c) the maintenance stage. The initiation stage (Weeks 1-2) aims to prepare participants for more intense aerobic exercise (i.e., by accumulating small improvements in cardiorespiratory fitness with light-to-moderate intensity exercise) and develop an orthopedic tolerance for exercise stress [31]. Following this period, participants will progress to the improvement stage of exercise training. This stage provides a gradual increase in the overall aerobic exercise stimulus (i.e., moderate-to-vigorous intensity), whereby participants realize substantial improvements in cardiorespiratory fitness [31] (Weeks 3-8). The final stage of exercise progression is the maintenance stage (i.e., vigorous intensity), which aims to maintain the levels of cardiorespiratory fitness that were developed during the improvement stage over the long-term [31] (Weeks 9-12). Consistent with ACSM recommendations, the intervention will not involve progression of both intensity and duration in a single exercise session. Such a gradual progression of exercise training is advantageous for deconditioned persons to safely achieve the benefits of aerobic exercise training [31].

Week	Sessions	Exercise Intensity	Exercise Duration	Training Stage
Baseline Testing				
1	1-3	40-50% VO ₂ R/HRR	15-20 min	Initiation
2	4-6	40-50% VO ₂ R/HRR	20-25 min	Initiation

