Sample Size Considerations. As described in the original application (i.e., R01HD091155-A1), we conducted a conventional power analysis using G*Power (Version 3.1.9.5) and estimated the appropriate sample size for detecting differences in follow-up SDMT scores, controlling for baseline score (Specific Aim 1). Using G*Power, this was accomplished using the 'F test' selection within the 'Test' family menu, and the Statistical Test of 'ANCOVA: Fixed effects, main effects and interactions'. The effect size ($\eta_p^2=0.11$) for the power analysis was computed from our pilot RCT¹² of TMWX training compared with a waitlist control condition on SDMT scores in persons with MS who had mild ambulatory disability, but not CPS impairment. That effect size was smaller than the effect sizes for thalamocortical RSFC outcomes, and thus was included in the main power analysis as a conservative approach. The power analysis included standard assumptions of alpha (0.05) and beta (0.80). The power analysis indicated that the minimal total sample size for testing group differences on follow-up SDMT scores, controlling for baseline scores should be 66 participants (33 per group). This supports our goal of recruiting 88 participants (44 per condition) as yielding adequate power, based on retention of 75% of the enrolled participants. The current application proposes a change of grantee organization whereby the final 72 participants will be enrolled at KF. We will explore the possible influence of study site on the outcomes in *post-hoc* sensitivity analyses. We expect that the effects of study site are likely negligible given the constants of the study team and standardized manuals of operating procedures that guide all study aspects.

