Specific Aim 1. The primary analysis will involve a statistically efficient step-down testing approach using ANCOVA models to examine changes in CPS and thalamocortical RSFC (i.e., examining group differences in follow-up outcomes, adjusting for baseline). As the primary study outcome involves CPS based on SDMT scores, we will first perform an ANCOVA model on follow-up SDMT score, with group (exercise or control) as a between-subjects factor and baseline SDMT score as the covariate. If statistically significant (i.e., $p<.05$), we will then assess the effects of the intervention on thalamocortical RSFC. This second step will involve performing two separate ANCOVA models on follow-up RSFC between the thalamus and right MFG and ACC, respectively, with group (exercise or control) as a between-subjects factor and baseline RSFC between the thalamus and right MFG and ACC, respectively, as the covariates. We will require an alpha of .05 (corrected for multiple comparisons) for significance for thalamocortical RSFC outcomes. The correction for multiple comparisons will be achieved by establishing a suitable voxel cluster-level threshold through Monte Carlo simulations (using the 3dClustSim program, part of the AFNI suite of image analysis programs). Based on our pilot work¹², we expect significant group differences in SDMT score and RSFC between the thalamus and right MFG and ACC, respectively, at follow-up after controlling for baseline scores, whereby participants who are randomly assigned to the exercise group will demonstrate greater SDMT scores and stronger thalamocortical RSFC at follow-up compared with those who are randomly assigned to the control group.

Specific Aim 2. We will examine RSFC between thalamus/right MFG, and RSFC between thalamus/ACC, respectively, as two potential mediators of the effects of TMWX training on CPS, consistent with the methodologies of Baron and Kenny⁸⁹ and MacKinnon et al⁹⁰. This statistical mediation approach is consistent with the proposed gold standard approach for examining exercise-related mechanisms of cognitive

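### Site is missing from the confirmatory SDMT and RSFC models although the trial moved institutions, apparently with a change of scanner; pre-specifying a site term is a near-free gain in precision

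*Combined protocol and SAP*

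**What the plan says.** **Two institutions.** Protocol 5.1.1 says that the study was partly completed at the University of Alabama at Birmingham and that 65 of the 88 participants will come from Kessler Foundation. The SAP (Statistical Design and Power, Sample Size Considerations) gives 72 at Kessler. The first site therefore holds 88 − 65 = 23 or 88 − 72 = 16 participants.

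**Imaging.** Protocol 5.2.1 describes one scanner: "The MR instrument that will be used is an FDA-approved Siemens Skyra 3T clinical imager housed in the Rocco Ortenzio Neuroimaging Center". The MRI protocol in 5.2.3.3 adds "customized sequences designed by [name] at Kessler Foundation". Nothing is said about the scanner or sequences used for first-site participants, or about harmonisation between scanners. All MRI processing and analysis is assigned to one blinded analyst (5.2.1).

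**Randomisation.** Protocol 5.2.4 says that "participants will be randomly assigned to either the exercise training or active control condition using concealment and a computerization". It mentions no strata or blocks.

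**Models.** The SDMT ANCOVA has group and baseline SDMT (protocol 5.3; SAP, Specific Aim 1). The RSFC ANCOVAs are fitted "with group (exercise or control) as a between-subjects factor and baseline RSFC between the thalamus and right MFG and ACC, respectively, as the covariates". The covariates to be added if they differ between groups (protocol 5.3; SAP, Statistical Analysis) do not include site.

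**Site.** The SAP says "We will explore the possible influence of study site on the outcomes in" post-hoc sensitivity analyses, and then gives its reason for expecting little: "We expect that the effects of study site are likely negligible given the constants of the study team and standardized manuals of operating procedures".

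**The concern.** RSFC is named as a primary outcome alongside SDMT. If the scanner changed with the institution, the RSFC level may differ systematically between first-site and Kessler participants. The reason given for expecting a negligible site effect concerns people and procedures. It is relevant to an oral test such as the SDMT but does not address scanner hardware or pulse sequences, and no figure supports it.

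Baseline RSFC, if taken on the same scanner as follow-up, removes an additive offset only in proportion to the baseline-to-follow-up slope. The rest stays in the error term. It also enters the group contrast if the arms happen to differ in their share of first-site participants. Because site is not among the conditional covariates, even an observed imbalance would not bring it into the confirmatory model.

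**Working it through.** **1. The plan's own figure.** Inputs from Sample Size Considerations: partial eta-squared 0.11, alpha 0.05, power 0.80, ANCOVA F test with two groups.
- f² = 0.11/0.89 = 0.1236, so d = 2√0.1236 = 0.70 residual SD.
- Noncentral F with λ = N f², df 1 and N − 2 − (number of covariates). With one covariate, power is 0.797 at N = 65 and 0.8030 at N = 66.
- 66/0.75 = 88. Both 66 and 88 reproduce.
- With site added (two covariates), power at N = 66 is 0.8028, so the required N stays 66.

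**2. What remains of a scanner offset after baseline adjustment.** The documents give no offset and no RSFC retest correlation, so these are assumptions. Let RSFC have within-site variance 1 at each visit, correlation r (0.3 to 0.7), and the same offset D (0.2 to 1.5 within-site SD) at both visits for first-site participants. With first-site share p, put v = p(1 − p).
- Pooled slope without a site term: b = (r + D²v)/(1 + D²v)
- Remaining offset: D(1 − b)
- Residual variance without site: (1 + D²v) − (r + D²v)²/(1 + D²v)
- Residual variance with site: 1 − r²

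For p = 23/88, v = 0.193. Example at D = 1, r = 0.5: b = 0.693/1.193 = 0.581; remaining offset 0.419; residual variance 0.790 against 0.750, a ratio of 1.054.

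| D | r | Remaining offset (SD) | Extra residual variance | Shift at 15:8 (residual SD) |
|---|---|---|---|---|
| 0.2 | 0.7 | 0.06 | 0.1% | 0.01 |
| 0.2 | 0.3 | 0.14 | 0.4% | 0.02 |
| 0.5 | 0.7 | 0.14 | 0.8% | 0.03 |
| 0.5 | 0.3 | 0.33 | 2.5% | 0.06 |
| 1.0 | 0.5 | 0.42 | 5.4% | 0.08 |
| 1.5 | 0.7 | 0.31 | 5.3% | 0.07 |
| 1.5 | 0.3 | 0.73 | 16.3% | 0.12 |

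With 16 first-site participants (v = 0.149), the extra variance runs from 0.1% to 13.5%.

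**3. Chance imbalance.** The last column uses a 15:8 split of 23 first-site participants, a difference in share of 15/44 − 8/44 = 7/44 = 0.159. The shift is 0.159 × remaining offset/√(1 − r²). The probability of 15:8 or worse in either direction is 0.21 under free allocation (binomial, 23, 0.5) and 0.14 if the arms are fixed at 44:44 (hypergeometric). Blocking would lower it further.

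**4. Power and type I error by simulation.** N = 66, 17 at the first site, effect 0.70 residual SD, both visits on the same scanner, unstratified allocation, 4,000 runs per setting.
- At r = 0.3, power without and with a site term is 0.791 and 0.796 (offset 0.5), 0.767 and 0.793 (1.0), 0.730 and 0.781 (1.5).
- At r = 0.8 the difference is at most about 0.6 points, within simulation error.
- Type I error without the site term is 0.048 to 0.056.

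The planning effect belongs to SDMT, so its use for RSFC is illustrative.

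**The case against.** The strongest reply is that a randomised comparison adjusted for baseline is valid without a site term, and that the likely loss is small. That stands. Other parts of the reply also stand:
- The plan's own position, a negligible site effect, is the bottom of the range above, where the extra variance is 0.4% or less.
- Last observation carried forward makes a dropout's follow-up equal the baseline, which carries the offset over in full. At 25% dropout unrelated to site or RSFC, r of 0.3 to 0.7 becomes 0.475 to 0.775. For offsets of 0.5 to 1.5 SD, the extra variance then falls from 1%–16% to 0.6%–11%.
- The SAP says that the pilot effects on RSFC were larger than the SDMT effect, so a shift matters less in relative terms.
- Nothing here quantifies a site effect on SDMT, where a constant team and manuals are a reasonable argument.

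Several stronger readings are tempting, but the documents do not support them:
- *First-site participants were certainly scanned on another machine.* This is likely, but it is inferred from the fact that only the Kessler scanner is described.
- *The randomisation ignored site.* Section 5.2.4 is silent on strata and blocks, which is not the same. Since the sites enrolled in sequence, ordinary blocking would already limit site imbalance.
- *The clinical team changed.* The study neurologist's name and affiliation are removed, so this cannot be checked.
- *The plan leaves open which result stands.* It names the primary model and labels site a sensitivity analysis, and a sensitivity analysis does not compete with the primary model.
- *The Aim 2 mediator is contaminated.* Aim 2 uses change scores, in which an additive offset cancels if both scans used the same scanner.

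What the reply does not answer is why a known design factor, which apparently coincides with a scanner change, should be left out of the confirmatory RSFC model on an unsupported expectation when including it costs almost nothing.

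**Conclusion.** The point holds as a modest, near-free improvement, not as an error that invalidates the analysis. Omitting site does not inflate type I error. It gives up some precision and leaves the RSFC contrast exposed to chance site imbalance. The size rests on assumed offsets (0.2 to 1.5 SD), assumed correlations (0.3 to 0.7) and both scans of a participant being on the same scanner: about 0.1% to 16% extra residual variance, and at a 15:8 split a shift of about 0.01 to 0.12 residual SD against a planning effect of 0.70. A reader might infer a much larger power loss, for example to 0.651 at N = 66. That figure requires 1.5 residual SD of site difference to survive baseline adjustment in full, which nothing in the documents supports. Equally, nothing in them shows that the scanner difference is negligible.

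**What to change.** - In protocol 5.3 and SAP Specific Aim 1, pre-specify site (first institution versus Kessler) as a fixed factor in the confirmatory RSFC ANCOVAs, including the voxel-wise model, and in the SDMT ANCOVA for consistency.
- In Sample Size Considerations, replace the post-hoc site exploration and its supporting expectation with this rule. Report the model without site as the sensitivity analysis, and keep site-by-group descriptive.
- In 5.2.4, state whether allocation is blocked or stratified. If it is not already blocked, use a separate blocked list for the remaining Kessler allocations.
- State which scanner and sequences were used for first-site participants, and reconcile the 65 and 72 Kessler counts.
- A site term in the Aim 2 change-score regressions is optional.

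Cost: wording, one degree of freedom, and possibly a new allocation list. No new data are needed and the required sample size does not change.

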5.2.7 Follow-up Testing. Within 48 hours following the completion of the last treadmill walking exercise training/stretching-and-toning session, the Project Coordinator will contact the participant and schedule them for follow-up testing. As is the case for baseline, this will occur across 2 visits that will be separated by a 2-day period. The first Follow-Up Visit will occur at the Kessler Foundation, and the second Follow-Up Visit will occur at the Rocco Ortenzio Neuroimaging Center at Kessler Foundation. Procedures for Follow-Up Visits 1 and 2 will be identical to that of Baseline Visits 1 and 2. Participants will be remunerated \$100 at the conclusion of Follow-Up Visit 2 in the form of a gift card.

5.3 Analysis. The data analyses will be overseen by a biostatistician (i.e., [name] at Pythagoras, LLC) and follow intent-to-treat principles (i.e., include all persons once randomized regardless of adherence and/or compliance). In the case of a drop-out, missing data will be imputed by carrying the last observed value forward. We further will perform exploratory data analyses in only those who completed follow-up testing (i.e., completer's or per protocol analysis) and in those who demonstrated good adherence (i.e., attended at least 83% of sessions) and compliance [69]. The analytic plan will account for several potential confounders of the effects of progressive TMWX training on the outcome measures; these confounders include MS duration, BMI, age, sex, T₂-lesion volume, and relapse rate, if those variables differ between groups. Further, all study data are entered and analyzed in SPSS version 25 (IBM Inc., Armonk, NY).

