Statistical Analysis. The data analyses will be overseen by [name] and follow intent-to-treat principles (i.e., include all persons regardless of dropout). In the case of a drop-out, missing data will be imputed by carrying the last observed value forward. We further will perform exploratory data analyses only in those who completed follow-up testing (i.e., completer's or per protocol analysis) and in those who demonstrated good adherence (i.e., attended at least 83% of sessions) and compliance. The analytic plan will account for several potential confounders of the effects of progressive TMWX training on the outcome measures. These include MS duration, BMI, age, sex, cognitive reserve, T2-lesion volume, and relapse rate. If these variables differ between groups, they will be included as additional covariates in the following analyses.

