Analysis by Race/Gender. We anticipate that 70% of participants will be female and 70% will be Caucasian. We will test the effects of gender and race on the intervention effects, and if there are interactions, we will separately analyze by gender/race to explore the specific effects of the variables on the outcomes. We do recognize that we will not likely enroll sufficient numbers of male participants or participants of Hispanic ethnicity and or other races to make meaningful comparisons.

Treatment of Missing Data. We conservatively plan for approximately 25% attrition based on a previous large RCT of 6-months (i.e., a longer intervention period than the proposed study) of multimodal exercise training versus a stretching-and-toning control condition on mobility outcomes in persons with moderate-to-severe MS-related ambulatory disability in our laboratory⁵⁶. In that study, the adherence rates for both the exercise and stretching-and-toning conditions were upwards of 75%, despite a significant barrier to participation being the inclusion of persons with substantial ambulatory disability. Of note, those adherence rates are *lower* than the overall average adherence rates for exercise trials involving persons with MS, based on a recent systematic review (i.e., upwards of 84% for both exercise and control conditions)⁵⁷. Nevertheless we have plans for

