exploring and examining the impact of such losses, as we could have upwards of 25% drop-out, given that this sample includes persons with objective CPS impairment. Initially, analyses will be done on the data set using last observation carried forward and then on the actual data collected (case-wise deletion), followed by multiple imputation for missing data. All analyses at present are planned using SPSS software (version 25 or higher), although as new options continue to evolve with SAS or R; these will be considered if there are new tools for imputation that will help understand the impact of missing data. We believe that these imputations should involve fewer than 15% of the participants, which then should have minimal impact on the analyses. However, it is important to assess this from a best case and worst case scenario and if the results are consistent, then we can be more confident of our findings. If these analyses yield differing results – more exploratory analyses are required to understand if the differences in the outcomes are coming from the control condition or the intervention condition. If the control condition, the implications can be examined in one way and if the intervention condition, it is likely to add cautionary notes to the findings.

Interim and Final Analysis. We do not plan any interim efficacy or futility analyses. The study team will work together for publications on the protocol, fidelity monitoring plan, as well as the primary study outcomes.

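### The intent-to-treat rule for SDMT is baseline carried forward, and no other analysis is named to open the step-down; the multiple imputation already planned should be made primary

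*Combined protocol and SAP*

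**What the plan says.** - **Missing-data rule.** Protocol 5.3 and the SAP's Statistical Analysis paragraph both state: "In the case of a drop-out, missing data will be imputed by carrying the last observed value forward". The protocol's intent-to-treat set is to "include all persons once randomized regardless of adherence and/or compliance". Both texts make the completer and good-adherence analyses exploratory.
- **Further analyses.** The SAP's Treatment of Missing Data paragraph gives a sequence. LOCF and the observed data come first and second: "Initially, analyses will be done on the data set using last observation carried forward and then on the actual data collected (case-wise deletion"). The third and last step in that order is "followed by multiple imputation for missing data". It adds that "it is important to assess this from a best case and worst case scenario" without defining either case. If results differ, "more exploratory analyses are required to understand if the differences in the outcomes are coming from the control condition or the intervention condition". Protocol 5.3 does not mention multiple imputation.
- **Expected losses.** The SAP plans for about 25% attrition, but also says: "We believe that these imputations should involve fewer than 15% of the participants".
- **Timing.** The Abstract and 5.2.2 give one assessment before and one after the intervention.
- **Gate.** The SDMT ANCOVA comes first. Under SAP Specific Aim 1, thalamocortical RSFC is assessed only if it is significant. Under protocol 5.3, formal testing ends at the first non-significant result.
- **Sample size.** The SAP needs 66 participants for 80% power and enrols 88, assuming 75% are retained.

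**The concern.** With a single follow-up, the last observed SDMT of a dropout is the baseline SDMT. Carrying it forward assigns that person no change and then counts the value as real data. If people who leave the exercise arm would have gained something, a true effect is diluted. If scores rise in both arms for reasons unrelated to treatment, dropouts are denied that rise, so the arm contrast also depends on which arm loses more people.

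Some common rise is plausible. Protocol 5.2.3.1 admits only people whose baseline SDMT is at least 1 SD below the norm, and scores selected for being low tend to regress upward. Alternate forms limit practice effects, not regression to the mean.

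All further formal testing depends on this one test. Three analyses are planned, none is named as the one that opens the gate, and there is no rule for when they disagree. The LOCF rule is not limited to any aim, so on its face it also reaches the RSFC models and the Aim 2 change scores. There, a person missing both follow-up measures would enter as an artificial pair of zeros.

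**Working it through.** **1. The plan's own figure.** Partial eta-squared 0.11 gives f² = 0.11/0.89 = 0.124 and f = 0.352. For two equal arms the difference is D = 2f = 0.703 residual SD. Noncentral F with 1 and N-3 degrees of freedom and noncentrality N × f² gives power 0.797 at N=65 and 0.803 at N=66. Then 66/0.75 = 88. The figures reproduce. They describe 66 observed follow-ups with the undiluted effect, not 88 people of whom 22 are carried forward. With all 88 observed, power would be 0.903.

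**2. What LOCF estimates.** Let dT and dC be the exercise and control dropout rates, c the change common to both arms, and θ the share of D that exercise dropouts would have gained. With dropout random within arm:
- mean change under LOCF: exercise (1-dT)(c+D), control (1-dC)c;
- LOCF difference = (1-dT)D + (dC-dT)c;
- effect in all randomised = (1-dT)D + dT·θ·D;
- bias = (dC-dT)c - dT·θ·D.

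The documents do not give θ. At equal 25% dropout LOCF gives 0.75 × 0.703 = 0.53. The all-randomised effect is 0.70, 0.62 or 0.53 for θ = 1, 0.5 or 0, so LOCF is too small by 25%, 14% or 0%.

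**3. A plausible c.** Assume a retest correlation ρ of 0.7-0.9, no practice gain, and an MS mean 1 to 1.44 SD below the norm. The 1.44 comes from reading the Literature Review's 67% as the share below -1 SD, although that figure is for cognitive impairment in general. With baseline truncated at -1 SD, selected people average 0.80 SD (mean at -1) or 0.54 SD (mean at -1.44) below the MS mean, and c = (1-ρ) × that shortfall. The range is 0.1 × 0.54 = 0.05 to 0.3 × 0.80 = 0.24 population SD. Dividing by √(1-ρ²) gives 0.12-0.34 residual SD.

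**4. Unequal losses.**
- 13 exercise v 9 control of 44 (30%/20%): 0.705 × 0.703 - 0.091c = 0.50 at c = 0, falling to 0.46 at c = 0.34.
- 9 v 13: 0.795 × 0.703 + 0.091c = 0.56 at c = 0, rising to 0.59 at c = 0.34.

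**5. Power.** Simulated ANCOVA, 44 per arm, D = 0.70, two-sided 5%, with and without the common change:

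| Dropouts, exercise v control | LOCF estimate | LOCF power | Multiple imputation power |
|---|---|---|---|
| 25% risk in each arm | 0.53 | 74-78% | 78-79% |
| 15% in each arm | 0.59-0.60 | 81-84% | 84% |
| 13 v 9 | 0.46-0.50 | 63-73% | 78-79% |
| 9 v 13 | 0.56-0.59 | 82-85% | 78-79% |

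Observed-data ANCOVA gives 79-80% at 25%. Multiple imputation (arm and baseline SDMT only) estimates 0.70 for either unequal split.

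**6. Direction when control loses more.** At 9 v 13 the bias is zero when θ = 0.091c/(0.205 × 0.703) = 0.63c, that is θ = 0.08-0.21. Above that, LOCF still understates the effect. In a 6 v 16 stress case it gives 0.63-0.68, still below 0.70.

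**7. Type I error.** Two-sided error is about 5% at equal dropout and at 30%/20%, and 5-7% at 36%/14%. If the larger loss (36%) is in control, claims in favour of exercise are 3.4-5.8% (nominal 2.5%) with the common rise and about 2.5% without it.

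**8. The reverse risk.** If 25% drop out and would have gained nothing (θ = 0), multiple imputation still estimates 0.70 against a true 0.53: 0.70/0.53 = 1.33, a third too large. Imputing exercise dropouts at the control mean returns 0.53, with 58% power.

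**The case against.** The plan is not silent: case-wise deletion, multiple imputation, extreme cases and a check of which arm drives any difference are all foreseen. At the losses the SAP expects, LOCF keeps more than 80% power. In the earlier trial it cites, "the adherence rates for both the exercise and stretching-and-toning conditions were upwards of 75" per cent, so a strong imbalance is not the central expectation. LOCF is exact at equal dropout if dropouts would have gained nothing, the very case where multiple imputation overstates. All of this stands, and it limits the point to which analysis has primary status.

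Four stronger readings are tempting but not supported:
- **That the SAP says LOCF opens the gate.** No single sentence does. It is the natural reading of the intent-to-treat rule, the exploratory status of completers and the order of the sequence.
- **That LOCF always works against the arm losing more.** When control loses more, the common-change term pushes toward exercise. The net bias favours exercise only if there is no true effect or θ is near zero; otherwise it offsets part of the shrinkage.
- **That chance imbalance is a further harm.** At 25% risk in both arms, a gap of four or more occurs in 39% of trials, but exercise is the arm losing more in only 19%. Such gaps are already averaged into the 74-78% power.
- **That false positives are a general problem.** Larger assumed common changes produce larger errors: at 0.70 residual SD, an 18 v 4 split gives 19-20%. That is about twice the top of the range derived above, and nothing in the documents supports it.

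**Conclusion.** The point holds as a should-fix. The stated rule sets every dropout's SDMT change to zero, and no other analysis is named to open the step-down. The main consequence is a diluted estimate: 0.53 instead of 0.70 at 25% dropout if dropouts would have gained as much as stayers, and no dilution if they would have gained nothing. Average power loss is small (about 1-5 points at 25%), but the same true effect meets a gate with 63-73% or 82-85% power depending on which arm loses four more people. Type I error is essentially intact outside the 36%/14% stress case.

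The mechanism follows from the documents. Confidence in the sizes is only moderate: retest correlation, common change, unequal splits, random dropout within arm and the MS mean are assumptions. The sizes concern SDMT only. The regression argument does not extend to RSFC, on which nobody is selected.

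**What to change.** Before unblinding, by a dated and justified SAP change (the trial is already under way):

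1. Name the planned multiple imputation as the primary SDMT analysis that opens the step-down: ANCOVA within imputations, with arm and baseline SDMT in the imputation model. Site and other baseline cognitive scores are optional; the figures above did not include them.
2. Move LOCF and case-wise deletion to sensitivity analyses.
3. Replace the undefined worst case with a control-mean or delta-adjusted analysis of exercise dropouts, reported beside the primary result.
4. Report dropout by arm.
5. For RSFC and the Aim 2 change scores, use observed pairs rather than carried-forward values. Multiple imputation was not evaluated for the voxel-cluster analysis.
6. Align protocol 5.3 and the SAP's Statistical Analysis paragraph with Treatment of Missing Data.

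The cost is slightly more analysis work and a missing-at-random assumption, which item 3 puts to the test. No new data are needed. The gain is in the estimate and in protection against unequal dropout, more than in power.
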